- List all personnel involved with this research who will have contact with human subjects or with their identifiable data. All personnel listed here must complete CITI training before this application will be processed.

NAME	FACULTY OR STAFF	GRADUATE STUDENT	UNDERGRAD STUDENT	ROLE ON PROJECT
[name]				Principal Investigator
[name]				Oxford Surgical and Bariatric Clinic, LLC site manager
				
				
				

If more space is needed to list project personnel, please submit Appendix A found on the ORSP Compliance Forms page.

OFFICE USE ONLY

APPLICATION TO CONDUCT RESEARCH WITH HUMAN SUBJECTS

ABSTRACT: Briefly summarize your project using non-technical, jargon-free language that can be understood by non-scientists. Include: (1) a statement of the research question and related theory supporting the reasons for, and importance of, the research; (2) the ages and characteristics of your proposed subjects and how you will recruit them; (3) the research design; and (4) a description of the procedure(s) subjects will undergo. Limit to the space below, using no less than a 12 point font. See Instructions (page 1) for a link to examples.

1. Objective: to assess the health and economic outcomes (weight lost, change in control of chronic diseases such as diabetes, quality of life, work productivity, health care cost, etc) associated with bariatric (weight-loss) surgery for 200 severely obese patients who undergo bariatric surgery as part of the Mississippi State Employees' Life and Health Insurance Plan's Obesity Treatment Program (OTP).

2. Patient Characteristics: Inclusion criteria: Eligible bariatric surgical candidates who are enrolled in the OTP (100 patients per year for 2 years). The Plan's criteria includes, but is not limited to 1) enrollment in the plan for at least 12 consecutive months prior to September 1, 2009; 2) completion of the HealthQuotient health risk assessment through the Plan's wellness and health promotion program; 3) a Body Mass Index (BMI) of >40 kg/m², or a BMI >35 kg/m² with two or more co-morbidities such as diabetes, hypertension, sleep apnea or asthma; 4) two or more physician-supervised weight loss attempts within the last 24 months; 5) age 18 years or older; and 6) consent to provide personal and medical information to the Plan. Prior to surgery, each site administers a psychiatric evaluation to ensure the patient is psychologically stable for surgery. Exclusion criteria: any patient who does not meet criteria above or who declines to participate. Surgeries will take place only at Certified Bariatric Surgery Centers of Excellence (COE), of which, there are currently 3 in the state. The 3 COEs exist with 4 outpatient medical offices (1 COE is composed of 2 independent surgeon practices) Patients will be recruited at each site once they are approved by the OTP.

3. Design: prospective, observational, multi-center, longitudinal study of outcomes and resource utilization associated with OTP. Estimates of obesity and comorbidities' impact will be obtained from the outpatient medical office for the COEs. Medical charts, databases and medical/pharmacy claims will be the source of information. Surveys on quality of life, productivity, and patient satisfaction will be administered directly to patients. Database claim information will be obtained in future and is not a part of current IRB application.

4. Procedures: After obtaining informed consent, patients will be administered surveys at baseline, as well as at follow-up visits. Additional data will be obtained via patient charts, databases, and medical/pharmacy claims.

1. PROJECT TITLE: Assessment of Outcomes Following Bariatric Surgery for Mississippi State Employees

If student project: dissertation thesis other:

Date dissertation or thesis proposal approved by committee: _____ (committee approval required)

2. PRINCIPAL INVESTIGATOR: [name]. [name]

Department: School of Pharmacy, Dept Pharmacy Practice Work [contact]

Mailing Address: [name] Home [contact]
[name]

E-Mail Address: [contact] [contact]

CO-INVESTIGATOR(S): name name

3. RESEARCH ADVISOR: _____ (required for student researchers)

Department: _____ Work Phone: _____

E-Mail Address: _____ Fax Number: _____

4. FUNDING SOURCE:

Is there funding for this project? Yes ⇨
 No

If Yes, is the funding:

Internal: ORSP Faculty Research Program
 Other:
 External: Pending/Agency:
 Awarded/Agency: Allergan

5. ANTICIPATED BEGINNING AND ENDING DATES OF HUMAN SUBJECTS CONTACT:

Beginning Date: 04/10/2010 (as soon as approved)
 Ending Date: 12/31/2013
 Not Applicable:

RESEARCH METHODOLOGY/PROCEDURES

6. CHECK ALL PROCEDURES BELOW THAT APPLY TO YOUR STUDY:

Pre-existing data ⇨ ⇨ ⇨

Source of data: Patient medical charts, BOLD Database, MS State Employee medical and pharmacy claims. Claims information not part of this IRB application.

Do data have identifiers? Yes No

- Observation
- Oral history
- Interview
- Focus group

Questionnaire or Survey ⇨ Anonymous? Yes No
 Distribution: Internet
 Mail
 E-mail
 In person
 Other:

Anonymous or Confidential?
 Anonymous means (1) the investigator cannot associate a subject with his/her data and (2) the data cannot identify a subject. Examples: Surveys with no names handed to an investigator are not anonymous; surveys placed by the subject in a group data envelope can be anonymous; surveys with no names and with demographic data that can identify a subject (e.g., the only African-American in a class) are not anonymous.

- Experiment/manipulation
- Treatment study
- Other:

Exercise ⇨ ⇨ ⇨ ⇨

Moderate
 More than moderate

- Videotaping
- Audio recording
- X-rays ⇨ ⇨ ⇨ ⇨

E.g. DEXA ~ contact Health & Safety for training requirements.

Collection/use of blood, urine, other bodily fluids, or tissues ** ⇨ ⇨ ⇨

Has IBC application been submitted? Yes No
 If Yes, has IBC application been approved? Yes No

** Requires IBC approval; see http://www.olemiss.edu/depts/research/compliance/compliance_forms.html#ibc. Contact Health and Safety for training requirements.

Use of drugs, biological products, or medical devices

7. DECEPTION OR OMISSION OF ELEMENTS OF CONSENT:

Do any of the following apply to your study?

- The study uses surreptitious videotaping.
- The study gives subjects deceptive feedback, whether positive or negative.
- The study uses a research confederate.
- The study has misleading or deceptive:
(1) study descriptions; (2) procedure explanations; and/or (3) survey instructions/rationales.

If you checked any of the above, please complete Appendix D.

PARTICIPANT INFORMATION

8. SUBJECT CHARACTERISTICS: Number: **200** Age Range: **18 & up** If under 18, parental consent is required.

9. BRIEFLY DESCRIBE SUBJECT POPULATION: **Obese adults with state insurance** E.g. 2nd grade students, college students, etc. Justify exclusion of any racial or gender group.

10. POTENTIALLY VULNERABLE SUBJECTS INVOLVED:

- Children/adolescents¹
- Mentally ill - outpatients
- Mentally ill - inpatients
- Cognitively impaired
- Elderly, if institutionalized
- Pregnant females
- Prisoners²
- HIV+
- Other:

Check all applicable groups.

¹ Complete Appendix B if applicable.

² Complete Appendix C.

11. RECRUITMENT PROCEDURES:

a. How will you recruit subjects? Check all that apply:

- Psych PSPM
- UM bulletin boards, where:
- Class announcements
- Letters to parents/guardians
- E-mail - specify groups:
[Mass e-mails to UM groups must: 1) be in plain text; 2) state "This study has been approved by UM's Institutional Review Board (IRB); and 3) be limited to 200 words.]
- Radio/TV/newspaper ads
- Other: **Patients who are approved for surgery at 4 sites as part of OTP will be enrolled. This application only pertains to Oxford Surgical & Bariatric Clinic, LLC**
[List all recruitment sites.]

Recruitment ad/e-mail/oral announcement is attached:

b. Are subjects in a subservient power relationship to investigators or to parties with an interest in the research, such as students in an instructor/investigator's class or employees of the investigator?

Yes No

If Yes, how will you ensure that their participation is truly voluntary?

Yes No

c. Describe incentives for subjects, if any (money, drawing, class points, etc.).

No incentives

d. List pro-rating for incentives for study drop-outs.

Not applicable

12. CONSENT PROCEDURES:

- Oral (attach script)
- Information letter – used in survey research (attach)
- Informed consent form (attach)
- Assent form for children or subjects with intellectual disabilities (attach)
- Not applicable

- Request waiver of *written* consent – justify:
- Request waiver of consent – justify:

Check all that apply.

If you plan to enroll non-English speaking participants, the consent form and assent document(s) must be translated into the appropriate language(s) and included with this submission.

For subject populations where competence to consent is highly questionable (e.g. some psychiatric populations), explain how competency will be determined and by whom.

13. WHERE WILL THE STUDY BE CONDUCTED?

- UM campus
- Local community: elementary/secondary school(s) or child care facility¹
- Local community: other – specify: **4 physician offices associated with 3 Certified Bariatric Surgery Centers of Excellence in Mississippi (Jackson, Oxford, Pascagoula). This application only pertains to Oxford Surgical & Bariatric Clinic, LLC.**
- Another U.S. location – specify:
- Another country² – specify:
- Not applicable
- Approval letter from another IRB attached
- Approval letter from other organization attached

Check all that apply.

¹Complete Appendix B.

²Complete Appendix E.

14. DESCRIBE ALL POSSIBLE RISKS TO SUBJECTS.

LIST STEPS TO MINIMIZE RISKS, INCLUDING EXPERIMENTER AND RESEARCH ASSISTANT TRAINING/EXPERTISE. For example, an emergency plan to handle potential adverse events for traumatic experience surveys or psychology research with children.

- a. **Physical: Patients have already chosen to receive surgery, which has risks, but this study doesn't increase risk.** n/a
- b. **Emotional: Surveys ask personal information, which may cause mild psychological stress, but no more than encountered in day-to-day life** n/a
Surveys will be administered at medical site, where patients could discuss with medical personnel. Patients will also be reminded that information shared is confidential.
- c. **Social/interpersonal: Surveys ask personal information, which may cause mild psychological stress, but no more than encountered in day-to-day life** n/a
Surveys will be administered at medical site, where patients could discuss with medical personnel. Patients will also be reminded that information shared is confidential.
- d. **Occupational: While subjects are employees, spouses, or retirees of the State, all medical information is confidential, so there should be no occupational risk.** n/a

- e. Financial: n/a
- f. Legal: n/a
- g. Other: n/a

15. WHAT ARE THE POTENTIAL BENEFITS, IF ANY, TO SUBJECTS (e.g. recognition of health risks, reduced stress, increased physical fitness, etc.) POTENTIAL BENEFITS DO NOT INCLUDE INCENTIVES OFFERED FOR PARTICIPATION.
 Patients who have bariatric surgery may have improved health, quality of life, and improved productivity at work. The administration of surveys, however, is expected to have minimal benefit to the subjects enrolled, however, by doing surveys, patients may recognize improved quality of life.

16. HOW WILL YOU MAINTAIN DATA CONFIDENTIALITY?

- All data are anonymous (go to next section).
- Data are confidential.
- Data kept in locked file cabinets.
- Data in locked room.

Anonymous or Confidential?
 Anonymous means (1) the investigator cannot associate a subject with his/her data and (2) the data cannot identify a subject.

THE IRB ENCOURAGES PERMANENT RETENTION OF DATA FOR POTENTIAL FUTURE USE BECAUSE THIS IMPROVES THE COST/BENEFIT RATIO.

When will data be de-identified? at time of collection n/a

PROJECT DESCRIPTION

17. DESCRIBE YOUR PROJECT IN THE SPACES BELOW.

Spaces will expand as you enter text.

a. Problem statement (including specific aims of your project):

To assess the health, humanistic and economic outcomes associated with bariatric surgery for 200 severely obese patients who have State insurance and who undergo bariatric surgery as part of the Obesity Treatment Program (OTP).

b. Brief literature review that points to a need for this research:

Mississippi has the highest rate of adult obesity in the nation at 32.8% in 2008, whereas, 10 years prior, the rate was 22.8%. Obesity has far-reaching effects on the health, health care resource use, and productivity of the population. Obesity-related co-morbidities and complications include coronary artery disease (CAD), hypertension, type 2 diabetes mellitus (T2DM), cancer, non-alcoholic fatty liver disease, dyslipidemia, and sleep apnea which increase the morbidity, mortality and cost of care associated with obesity. Increases in obesity in the US population parallel a substantial share of growth in health spending and continues to impose an economic burden on both public and private payers.

Studies currently exist which evaluate the costs and benefits of bariatric surgery on an obese population, but little information is available on a population with obesity rates as high as seen in Mississippi.

Additionally, in 2009, the State of Mississippi passed legislation that authorized bariatric surgery as a covered health benefit for state employees for a select obesity program. Continued coverage past 2011 will be contingent on outcomes from the project and funding availability.

As a result of this legislation, Mississippi's State and School Employees' Life and Health Insurance Plan (SSELHI Plan) will provide a two-year Obesity Treatment Program (OTP) for the treatment and management of obesity and related conditions. Under the OTP, the Plan will provide benefits for medically necessary bariatric procedures at certified Centers of Excellence (COE) in Mississippi for qualifying participants.

c. Description of procedures:

After approval for surgery by the OTP, patients will be invited to participate in this study at the physician office associated with a COE. This application is for the Oxford Surgical & Bariatric Clinic, LLC. After completion of Consent Form, patients will be asked to fill out surveys and their providers, medical staff and/or PI will assist in filling out data collection form at initial and follow-up visits. No direct intervention to the patient will occur. Some patients have already had surgery--for these patients will have the surveys administered at next follow-up, and chart reviews will be done to fill out Initial Visit and Follow-Up Visit Data Collection Forms. Database claim information is not part of this IRB application, but will be

done in future to obtain economic outcome information.

d. Measures:

SURVEY/TEST/QUESTIONNAIRE (e.g. WAIS)

NAME AND ACRONYM	IS THERE PUBLISHED PSYCHOMETRIC SUPPORT?
1 Work Productivity and Activity Impairment Questionnaire: General Health V2.0 (WPAI: GH)	 Yes  No
2 Impact of Weight / Quality of Life-Lite (IWQOL-Lite)	 Yes  No
3 Patient History Survey	 Yes  No
4 Patient Satisfaction Survey	 Yes  No
5	 Yes  No

OTHER MEASURES (e.g. heart rate)

NAME

- 1 **Prevalence of hypertension, control of hypertension (as measured by blood pressure) and use of medication for hypertension (drug[s], dose)**
- 2 **Prevalence of type 2 diabetes mellitus (DM), control of DM (as measured by A1c) and use of medication for DM (drug[s], dose)**
- 3 **Prevalence of dyslipidemia, control of dyslipidemia (as measured by lipid levels) and use of medication for dyslipidemia (drug[s], dose)**
- 4 **Prevalence of sleep apnea and sleep apnea score**
- 5 **Prevalence of other obesity-related complications, including but not limited to CAD, asthma, gastroesophageal reflux disease (GERD) and control of these diseases**
- 6 **Serum creatinine and liver function enzymes, when available in medical charts**
- 7 **Incidence of nutritional deficiencies and use of medication to treat deficiencies**
- 8 **Incidence of device or surgery-related adverse events**
- 9 **Outpatient medication costs***
- 10 **Hospitalization costs***
- 11 **Office visit costs***
- 12 **Emergency room costs***

*these items will be part of research in future and are not part of current IRB application.

e. Provide a numbered step-by-step list of all procedures, starting with recruitment. Elaborate on more complex items. Attach scripts of procedural instructions to subjects. See Instructions (page 1) for examples.

- 1 **Mississippi's State and School Employees' Life and Health Insurance Plan (SSELHI Plan) will determine which 200 patients will have surgery as part of the Obesity Treatment Program (OTP). 100 patients were approved in 2009, and 100 more will be approved in 2010. Patients approved for the OTP will work with the surgery team to chose the type of surgery best for the patient. Once the patient is approved for the OTP, then their participation with this study can begin.**
- 2 **At the initial visit for surgery consultation, the patient will be asked if they are willing to participate in this study. If patient consents, then they will fill out the consent form with the assistance of someone at the COE ([name]). This person has been trained in admisistration of surveys by the PI. Once the Consent Form has been signed, the patient will answer surveys (Patient History Survey, WAPI: GH, IWQOL-Lite). After this visit, medical personnel in the COE ([name], with the assistance of the PI when available), will fill out the Initial Visit Data Collection Form. The information for the Initial Visit Data Collection Form will come from the patient's medical record and/or the BOLD database (a database all COEs use to collect information on all surgery patients at the site).**

If the patient has had surgery already, the Patient History Survey will be administered to the patient at the

next available visit.

3. **Soon after the patient has surgery, the Peri-surgery Data Collection Form will be filled out by medical personnel at the physician's office ([name]). If needed, PI will assist in completion of this form.**
 4. **At follow-up visits near 6 months, 12 months, and 24 months post-surgery at the physician office, the patient will fill out the IWQOL-lite, WPAI:GH, and Patient Satisfaction surveys. After these follow-up visits, medical personnel at the COE (with the assistance of PI when available), will fill out the Follow-up visit Data Collection Form. Information for this form will also be found in the patient chart and/or BOLD database.**
 5. **If the patient has an adverse event at any time during the study, an adverse event form will be filled out by medical personnel and/or PI.**
 6. **At study closure, or if patient wishes to withdraw from the study at any time, the Withdrawal/End of Study form will be filled out.**
 7. **Each patient will also have a State Employee Bariatric Surgery Project Checklist, which will be filled out by [name] to ensure study methods are followed correctly.**
 8. **After the patient has signed the consent form, study personnel will collaborate with CareAllies, which serves as the disease management program for the Mississippi State and School Employees' Life and Health Insurance Plan State of Mississippi. Via this collaboration, medical and pharmacy claims will be reviewed for the patient to collect information (costs) of pharmacy utilization, medical visits, emergency room visits, and hospitalizations.* This part of the study is not a part of the current IRB application, but will be done at a later time.**
- f. **Data analysis methods:**
Statistical analysis: Descriptive statistics will be reported for each measure at baseline and at the 6, 12, and 24 month followup periods. We will use a generalized linear model for repeated measurements (generalized estimating equations) to assess the effect of bariatric surgery across followup periods. This approach will also be used to assess the effect of surgery type (Roux-en-y versus banding) while controlling for the effect of other variables. An alpha of 0.05 will be used to determine statistical significance.
- g. **Debriefing and/or feedback on test results (procedures, forms, scripts, and statements if applicable):**
N/A

ASSURANCES - CONFLICT OF INTEREST AND FISCAL RESPONSIBILITY

Do you or any person responsible for the design, conduct, or reporting of this study have an economic interest in, or act as an officer or a director of any outside entity whose financial interests may reasonably appear to be affected by this research?

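### Adverse events count as an outcome only when judged device- or surgery-related, although every adverse event gets a form and no attribution rule is stated

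*Combined protocol and SAP*

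**What the plan says.** **Outcome.** In section 17d, Other Measures, item 8 is "Incidence of device or surgery-related adverse events". It is the only item in that list that concerns adverse events as such.

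**Collection.** Section 17e, step 5, is wider. It applies "If the patient has an adverse event at any time during the study", and then "an adverse event form will be filled out by medical personnel and/or PI". Relatedness is not a condition for completing the form.

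**Other safety-relevant measures.** Item 7 is "Incidence of nutritional deficiencies and use of medication to treat deficiencies" and item 6 is "Serum creatinine and liver function enzymes, when available in medical charts". Neither is worded in terms of relatedness.

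**Design.** The abstract (item 3) describes a "prospective, observational, multi-center, longitudinal study of outcomes and resource utilization associated with OTP". All patients are approved for surgery under the Obesity Treatment Program, and the patient and surgery team choose the procedure (17e, step 1). No blinding is described.

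**Analysis.** Section 17f gives descriptive statistics for each measure. It also uses generalized estimating equations (GEE) to assess the effect of surgery type, Roux-en-Y versus banding, with adjustment for other variables, at an alpha of 0.05.

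**Patients already operated on.** Section 17c says that some patients have had surgery before joining. For them, the Initial Visit and Follow-Up Visit forms are completed by chart review.

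**The concern.** The plan collects a wider set of events than it reports. An event judged unrelated gets a form and then leaves the only adverse-event outcome. What remains depends on a judgement for which the available text gives no definition, criteria or named assessor.

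Two features of the design make this judgement hard to check. No blinding is described, so whoever judges relatedness may well know the procedure. Every patient is operated on, so no unoperated group shows how often such events occur without surgery.

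Two things are at stake. The overall incidence of harm may be understated if related events are called unrelated. A Roux-en-Y versus banding comparison of item 8 may also show a difference, or hide one, because attribution differs between the procedures. Covariate adjustment would not remove this, because the error lies in the outcome itself. Section 17b says that continued coverage after 2011 depends partly on the project's outcomes, so the incidence may be read by decision-makers.

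**Working it through.** The plan states no adverse-event rate, power or sample-size calculation, so there is no figure to reproduce. The check has two parts.

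**1. The statements side by side**

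| Question | What the documents give |
|---|---|
| Which events get a form? | Any adverse event, at any time in the study (17e, step 5) |
| Which events count in the outcome? | Only those related to the device or surgery (17d, item 8) |
| Who completes the form? | Medical personnel and/or the principal investigator (PI) (17e, step 5) |
| Who judges relatedness, and by what rule? | Not stated in the available text |
| Is there independent or blinded review? | None described |
| Is there an all-event summary, or an outcome of any-cause readmission, reoperation or death? | None listed in 17d |

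If the plan is followed as written, events judged unrelated are recorded and then left out of the reported incidence.

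**2. Illustration of possible size (all inputs assumed)**

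*Overall incidence.* If a fraction m of truly related events is called unrelated, reported incidence = true incidence × (1 − m). For a true 20%:
- m = 0.10 gives 0.20 × 0.90 = 18%.
- m = 0.30 gives 0.20 × 0.70 = 14%.

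*Comparison by procedure.* Let p be the all-event risk, equal in both procedures, and let a₁ and a₂ be the proportions of events called related. Reported incidence is q = p × a. Any gap between a₁ and a₂ is taken to be judgement alone. The test is a two-sided, pooled-variance comparison of two proportions at 0.05 with n per procedure, a simple stand-in for the planned GEE.

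- SE₀ = √[2 q̄(1 − q̄)/n], where q̄ is the mean of q₁ and q₂
- SE₁ = √[q₁(1 − q₁)/n + q₂(1 − q₂)/n]
- P(reject) = Φ[(d − 1.96 SE₀)/SE₁] + Φ[(−d − 1.96 SE₀)/SE₁], where d = |q₁ − q₂|

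For p = 0.30, n = 100, a = 0.70 versus 0.50:
- q = 0.21 and 0.15; d = 0.06; q̄ = 0.18
- SE₀ = √(2 × 0.18 × 0.82/100) = 0.0543, so 1.96 SE₀ = 0.1065
- SE₁ = √(0.001659 + 0.001275) = 0.0542
- (0.06 − 0.1065)/0.0542 = −0.86, giving P(reject) of about 0.20

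| Called related | Reported incidence (p = 0.30) | P(reject), p = 0.30, n = 100 | Range over p = 0.20–0.40 and n = 50–100 |
|---|---|---|---|
| 60% vs 60% | 18% vs 18% | 0.05 | 0.05 |
| 70% vs 50% | 21% vs 15% | 0.20 | 0.09–0.26 |
| 80% vs 40% | 24% vs 12% | 0.60 | 0.23–0.76 |

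A milder case: with a true related-event rate of 20% in both procedures, and 95% versus 75% of those events attributed, the reported rates are 0.20 × 0.95 = 19% and 0.20 × 0.75 = 15%. With 100 per procedure the standard error of the difference is √(0.19 × 0.81/100 + 0.15 × 0.85/100) = 0.053. The false 4-point gap is then about 0.75 standard errors.

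The 200 patients are the programme total, and this application covers one clinic. The split by procedure is not given, so 100 per procedure is itself an assumption.

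**The case against.** Several points on the other side are sound and limit the claim.

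- **A reader might infer that safety as a whole is measured only through related events.** The documents do not support that: items 6 and 7 are safety-relevant and need no relatedness call.
- **A reader might infer that clinic staff or the PI decide relatedness.** Step 5 says who completes the form, not who attributes the event. The supportable statement is that no assessor or rule is named.
- **The forms are not in the available text.** The adverse event, peri-surgery, follow-up and end-of-study forms may hold relatedness criteria, or fields for reoperation, readmission or death. Charts and the BOLD database may hold them too. One cannot conclude that these data go uncollected, only that 17d does not list them as outcomes.
- **Utilisation data are planned.** Step 8 foresees a claims review covering hospitalizations and emergency visits, with no relatedness filter. It is deferred to a later application and framed as costs, so it answers the point only in part.
- **No dedicated safety comparison is specified.** Section 17f does not name adverse events when it describes the surgery-type analysis. Item 8 falls under the descriptive statistics for each measure, and may or may not enter the GEE.
- **The magnitudes are assumed,** and in the milder case the bias is smaller than sampling error. Procedure is also chosen rather than randomised, so confounding affects the comparison whichever count is used.
- **An all-event count has its own weaknesses.** It includes background illness, which can dilute a real difference between procedures, and it still depends on staff recording events.

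The mismatch between items collected and items reported remains. Even if a form defines relatedness well, item 8 still leaves out events judged unrelated. The last objection is a reason to report both counts, not to keep only the related one.

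**Conclusion.** The point holds for adverse events. They are listed as an outcome only when related to the device or surgery, although a form is required for all of them. With no attribution rule or assessor in the available text, no blinding described and no unoperated group, the reported incidence rests on a judgement that cannot be checked. The same applies to any Roux-en-Y versus banding comparison of it.

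The size and direction of any bias are unknown. Under the assumptions above, it runs from negligible to a false-positive rate well above 5%: about 0.09–0.26 for 70% versus 50% attribution, and 0.23–0.76 for 80% versus 40%. These figures show what attribution could do. They are not evidence that it does so here, and the documents do not show that attribution differs between bands and bypass.

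This is an inexpensive improvement to an outcome definition and does not undermine the study.

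**What to change.** 1. Reword item 8 of section 17d along these lines: *Incidence of all adverse events regardless of attribution, with device or surgery-related events reported as a subset.*
2. Show both counts by surgery type. Neither should be the sole basis for comparing the procedures.
3. Report any-cause readmission, reoperation and death where the existing forms, charts or BOLD database already record them.
4. State the event window for patients operated on before consent. Section 17c covers them by chart review and mentions only the Initial Visit and Follow-Up Visit forms, so it is unclear whether their earlier events would reach a step 5 form.

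The cost is one more table, plus some chart checking if the forms do not identify readmission, reoperation or death. The all-event count will include background illness and will still depend on staff recording events; the related subset beside it lets the reader see both. No change to patient care is involved.

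### Item 17f names GEE with no working correlation or missing-data method, so outcome-related missed visits and absent pre-surgery surveys could misstate the size of the 24-month survey change

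*Combined protocol and SAP*

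**What the plan says.** Item 17f plans descriptive statistics at each visit, one inferential method, and an alpha of 0.05. The method is: "We will use a generalized linear model for repeated measurements (generalized estimating equations) to assess the effect of bariatric surgery across followup periods". The same model serves the comparison of procedures: "This approach will also be used to assess the effect of surgery type (Roux-en-y versus banding) while controlling for the effect of other variables". Item 17f names no working correlation, no missing-data method and no sensitivity analysis.

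Four other places bear on this:

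- **Surveys need attendance.** Item 17e step 4 says: "At follow-up visits near 6 months, 12 months, and 24 months post-surgery at the physician office, the patient will fill out the IWQOL-lite". WPAI:GH and the satisfaction survey are completed at the same visits, and satisfaction has no baseline. Item 14 also places survey administration at the medical site.
- **Some baselines do not exist.** Item 17c says: "Some patients have already had surgery--for these patients will have the surveys administered at next follow-up". Chart review completes the data collection forms for these patients, but it is not described as a source of survey scores.
- **Timing and scope.** Item 17e step 1: "100 patients were approved in 2009, and 100 more will be approved in 2010". Item 5: "Beginning Date: 04/10/2010 (as soon as approved". Item 13: "This application only pertains to Oxford Surgical & Bariatric Clinic, LLC".
- **Clinical data have a second source.** On the follow-up form, step 4 says: "Information for this form will also be found in the patient chart and/or BOLD database".

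**The concern.** The working correlation is often treated as a matter of efficiency only. That holds with complete data, or when loss is unrelated to outcome. When attendance depends on earlier results, the choice changes the estimate itself. With a separate mean for each visit and an independence correlation, GEE simply returns the mean of those who attended. The 24-month change is then the mean of 24-month attenders minus the mean of those with a baseline. These are partly different people, and absent pre-surgery surveys add to that mismatch without any drop-out.

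The study exists to describe outcomes, so the size of the change is its main product. It would look too large if poorer responders are lost and too small if better responders are lost. An unstated method can also be settled after the results are seen.

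**Working it through.** **Inputs from the documents.** Visits are at baseline, 6, 12 and 24 months; the model is GEE; alpha is 0.05 (taken as two-sided). No expected change, SD, attendance rate or power is given, so there is no figure of the plan's own to reproduce.

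**Assumed inputs.** One clinic with n=50; true change -14, -20 and -24 at 6, 12 and 24 months; baseline SD 15. The SD of individual change is 6, 8 and 10, with correlation 0.9 between adjacent visits and 0.81 from 6 to 24 months; residual SD is 3. Drop-out at 12 and 24 months has log-odds 0.7 or 1.2 per 8 units of previous change, giving 24-month retention of 74% or 57%. There were 600 simulation runs.

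**Step 1: estimated 24-month change (truth -24, all baselines present).**

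| Who is lost, retention | Independence GEE | Exchangeable GEE | Likelihood model |
|---|---|---|---|
| Poorer responders, 74% | -25.25 | -24.76 | -23.97 |
| Poorer responders, 57% | -27.15 | -25.95 | -23.95 |
| Better responders, 74% | -22.59 | -23.22 | -24.01 |
| Better responders, 57% | -20.65 | -22.05 | -24.03 |

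**Step 2: size of the bias.** Bias = estimate minus truth.

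- Independence: from 25.25 - 24 = 1.25 to 24 - 20.65 = 3.35 units.
- Exchangeable: from 24.76 - 24 = 0.76 to 24 - 22.05 = 1.95 units.

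The bias is additive: at the same retention and variances it does not shrink with the true change. The percentage therefore depends on the assumed change. For independence, 1.25/24 = 5% and 3.35/24 = 14%; for a change of 7.5 (0.5 baseline SD), 1.25/7.5 = 17% and 3.35/7.5 = 45%.

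**Step 3: detection.** With better responders lost and a true change of 7.5, the independence estimate is about 7.5 - 1.41 = 6.09 or 7.5 - 3.35 = 4.15. The simulated standard errors were 2.14 to 2.71. Detection is roughly Φ(estimate/SE - 1.96), which gives 61% to 81% for 6.09 and 33% to 49% for 4.15. Direct simulation gave 81% and 38%. Without bias and at the SE of 2.30 found under random loss, Φ(7.5/2.30 - 1.96) = 90%. For a 0.3 SD change, simulation gave 36% or 7%. For the assumed change of 24 the estimate stays at least 7.6 standard errors from zero.

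**Step 4: absent pre-surgery surveys.** With half lacking a baseline and purely random loss, the SE is 3.27 (independence), 2.10 (exchangeable) and 2.01 (likelihood), against 2.30, 1.73 and 1.70 with all baselines. If those patients also differ by 5 units, independence gives -21.57 or -26.54 (about 10% off), exchangeable -24.01 or -24.29 (about 1% or less) and likelihood -23.59 or -24.57 (about 2%).

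**Step 5: procedure comparison (25 per group, no true difference).** Outcome-related loss in one group only gives a false difference of 1.28 or 2.92 (independence), 0.87 or 2.06 (exchangeable) and 0.14 or 0.08 (likelihood). The same loss in both groups gives about 0. With an assumed true difference of -9.6 and one attendance rule for both groups, independence gives -9.0 or -7.8. That is 0.6/9.6 = 6% or 1.8/9.6 = 19% off, because unequal outcomes produce unequal loss.

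**Step 6: different assumptions.** A second simulation used correlation 0.6 between visits, log-odds 1.0 per SD of the previous result, and retention of about 71% or 53%. Independence was off by about 0.16 or 0.27 to 0.28 SD (exchangeable truth), or 0.10 or 0.19 SD (first-order autoregressive truth). Step 2 corresponds to 1.25/15 = 0.08 SD up to 3.35/15 = 0.22 SD. At n=200 under exchangeable truth, coverage of the 95% interval fell to 42% to 50%, or 10% to 19%. With no true change and poorer responders lost, the 5% test rejected in 50% or 84% of runs. Exchangeable GEE stayed at 0.97 to 1.05 for a true change of 1.0 SD.

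**The case against.** The strongest reply has three parts.

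**No evidence of outcome-related attendance.** This stands. A reader might infer that drop-out will follow results, but the documents neither say so nor give an attendance rate. The bias is conditional. The absent baselines are not: item 17c makes them certain for some patients.

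**Naming a working correlation would be enough.** This stands in part. Exchangeable GEE was 3% to 8% off for a change of 24, and close to the truth in the second simulation. But it leaves some bias when the true correlation is not exchangeable. Unstructured GEE was 1% to 3% off where it could be fitted, yet its matrix was not positive definite in 19% to 42% of n=50 runs, and in 65% to 81% with half lacking a baseline.

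**Chart and BOLD data fill gaps.** This stands for clinical measures, which are less exposed. It does not help the survey scores.

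Four stronger readings should be resisted:

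- Half the patients lack a baseline survey. The 100 approved in 2009 is a programme-wide count of approvals, not of operations. This clinic's share could be lower or higher, and the number is not stated.
- A real change will be missed, or detection is safe in any case. Either would need the expected change and its SD, which are not given.
- The procedure comparison is biased. It can be if outcome-related loss differs between procedures, but no passage says that it does.
- A likelihood model removes all bias. If loss depends on unseen values, it was still 3% to 9% off.

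**Conclusion.** The concern holds conditionally and is worth settling before analysis. Item 17f leaves open a choice that affects the estimate, for outcomes collected only from those who attend and with some baselines absent by design. Under the assumed inputs, the independence bias is about 1.3 to 3.4 units in either direction. The exchangeable bias is about 0.8 to 2.0 units, and the likelihood model is within about 0.05 when all baselines are present. How serious this is depends on the true change: modest at 24, substantial at 7.5. Detection is safe only if the change is large relative to its SD. The direction and rough size agreed under two sets of assumptions, but retention, drop-out dependence, variances, effect sizes and n=50 are all assumed.

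**What to change.** In item 17f:

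1. **Continuous outcomes, survey scores first.** Make a likelihood-based repeated-measures model the main analysis. Use baseline, 6, 12 and 24 months as responses, with categorical visit, surgery type and their interaction, and an unstructured covariance with a named fallback. Patients without a pre-surgery survey then still contribute, and loss that depends on observed results is handled. Satisfaction uses follow-up visits only.
2. **Binary outcomes.** Keep GEE, state the working correlation, and use multiple imputation first where values are still missing after chart and BOLD review. In a simulated n=50 case with a true rate of 50%, unweighted estimates were 57% to 69% or 43% to 31%, and imputed ones 49% to 51%. That is a best case, because the simulated data were normal.
3. **Reporting.** Give attendance by visit and surgery type, and the number without a pre-surgery survey.
4. **Optional.** Add a missing-not-at-random sensitivity analysis.

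The cost is modest programming, with no new visits or data. At n=50 the likelihood standard error was 0.6 to 0.8 times that of independence GEE, but up to about 1.1 times that of exchangeable GEE at 57% retention.
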